### 8.10.5.2 Definition of Dose-Limiting Toxicity (DLT)

Dose-Limiting Toxicity in an individual subject is defined as any Grade 2 or higher Adverse Event (AE) toxicity according to National Cancer Institute Common Terminology Criteria for Adverse Events, Version 3.0 (CTCAE – See Appendix 16.1) that is considered by the Investigator to be at least possibly related to study drug.

### 8.10.5.3 Definition of Maximum Tolerated Dose (MTD)

If dose escalation is stopped according to criteria of 8.10.4 and the Safety Review Committee does not decide to administer a dose lower than the level at which dose escalation was stopped and higher than the next lowest tested level, the next lowest tested level will be considered the maximum tolerated dose (MTD).

#### 8.11 Subsequent Cohort Dose Plan

Anticipated Dose Plan – Upon completion of Safety Review of experience to date, if the Safety Review Committee determines that there is no reason to do otherwise, the dose plan for the subsequent cohort is:

- Randomization and dosing proceed no sooner than 7 days after the last Day 1 dosing of the preceding cohort.
- Dose of study drug administered to subjects in the next cohort is the next higher dose anticipated by protocol (e.g., 1% Nu-3 solution dose cohort after 0.1% Nu-3 solution dose cohort).
- Ten subjects are randomized such that eight dose with Nu-3 and two dose with Placebo.
- A single subject is dosed at a given scheduled time.
- Dosing of successive subjects are separated in time by an interval that may vary between cohorts but must be at least 20 minutes. Safety Review Committee may specify this interval.

#### 9 SELECTION AND WITHDRAWAL OF SUBJECTS

Subjects with diabetic chronic foot ulcer and with a DUSS Score of 0 to 3, ulcerated area(s) of not more than two (2) ulcers between 0.5 to 6 cm^2, and no underlying DUSS Probing to Bone = "Yes" will be enrolled. This study will enrol 10 evaluable subjects per group in 5 groups for a total of 50 evaluable subjects. An evaluable subject is one who has received investigational product and has returned for the  $15 \pm 2$  Day follow-up visit. Up to approximately 55 patients will be enrolled in order to have a population minimum of 50 evaluable subjects at the end of the trial.

### 9.1 Inclusion and Exclusion of Subjects

To be included in this study, subjects must meet the following inclusion/exclusion criteria:

#### 9.1.1 **Inclusion Criteria**

- 1. Men and women between the ages of 18 and 85.
- 2. Voluntary written consent, given before performance of any clinical investigation-related procedure not part of standard medical care, and with the understanding that consent may be withdrawn at any time without prejudice to future medical care.
- 3. Non-hospitalized ambulatory subjects suffering from Diabetes mellitus, Type I or II
- 4. Diabetic foot ulcer(s) with a DUSS Score of 0 to 3
- 5. Ulcerated area(s) of not more than two (2) ulcers between 0.5 to 6 cm^2
- 6. Any female of child bearing age must consent to use medically acceptable birth control for the duration of the study
- 7. Female subjects must meet at least one of the following additional criteria:
  - d. Surgically sterile with bilateral tubal ligation or hysterectomy.
  - e. Post-menopausal for at least one year.
  - f. If of child-bearing potential, practicing an acceptable method of birth control for the duration of the clinical investigation as judged by the Investigator, such as condoms, foams, jellies, diaphragm, intrauterine device or abstinence.
- 8. Subjects willing to undergo pre-and post-clinical investigation blood collection, physical exams and laboratory investigations..

#### 9.1.2 Exclusion Criteria

- 1. A DUSS Score above 3.
- 2. DUSS Probing to Bone = "Yes"
- 3. An ulcer area(s) greater than 6 cm^2 or more than two (2) ulcers

- 4. Any subject that has received systemic or topical antibiotics within the last seven (7) days
- 5. Any subject on topical antimicrobial treatment for their infected diabetic foot ulcer whose ulcer is responding to treatment
- 6. Any subject that would be unable to follow the protocol procedures, safely monitor the infection status at home, and return for schedule visits
- 7. Positive pregnancy test at Screening or Visit 2
- 8. Active infection as demonstrated by temperature > 37.5 °C and clinical features of active infection.
- 9. Known immunosuppression or taking immunosuppressive agents including systemic steroids.
- 10. History of severe co-morbidity with expected patient survival  $\leq$  6 months.
- 11. Pregnancy or lactation
- 12. Intake of investigational drugs within 28 days prior to enrollment.
- 13. History of concurrent condition that, in the Investigator's opinion, would jeopardize the safety of the subject or compliance with the protocol.
- 14. Likely inability to comply with the protocol or cooperate fully with the investigator and site personnel.
- 15. Unwillingness or language barrier precluding adequate understanding of the trial procedure or cooperation with trial site personnel.
- 16. Known or suspected active abuse of alcohol, narcotics or non-prescription drugs.
- 17. Other planned surgical procedures within 30 days prior to or 30 days post-index procedure.
- 18. Prior enrolment in this clinical trial

### 9.2 Withdrawal of Subjects

A subject must be withdrawn from the study prior to completion for any of the following reasons:

- Whenever the subject decides that it is in his/her best interest to withdraw
- Whenever the investigator decides that it is in the subject's best interest to be withdrawn
- An adverse event or illness which may, in the investigator's opinion, significantly affect the subject or study
- Non-compliance
- Sponsor administrative reasons.

Withdrawal of consent for follow-up should be accompanied by documentation of the reason for withdrawal. Withdrawal of consent for treatment should be distinguished from withdrawal of consent for follow-up visits and from withdrawal of consent for non-patient contact follow-up, e.g., medical records checks. Subjects requesting withdrawal should be informed that withdrawal of consent for follow-up will jeopardize the public health value of the study.

Subjects who withdraw should be explicitly asked about the contribution of possible adverse events to their decision to withdraw consent, and any adverse event information elicited should be documented.

Preferably the subject should withdraw consent in writing and, if the subject or the subject's representative refuses or is physically unavailable, the site should document and sign the reason for the subject's failure to withdraw consent in writing. The informed consent for the study should note that although a subject is free to leave the study and stop taking study medication, the investigators hope the patient will remain for follow up status evaluations.

Data from subjects who withdraw from the study will still be used in the statistical analysis. A decision to replace a withdrawn subject will be made on a case-by-case basis after discussions between the investigator, Medical Monitor, and Sponsor. Generally speaking, a subject who does not meet the definition of "evaluable" (i.e., received investigational product and has returned for the Day 2 follow-up visit) may be replaced. However, all subjects, whether withdrawn or not, will be included in ITT population for safety evaluations of Nu-3.

### 10 Investigational Products

### 10.1 Study Drug and Placebo

	Nu-3	Placebo			
	Xcelience LLC				
Manufacturer	[name]				
	[name]				
Route	Topical				
	0.1% Nu-3 in 0.9% saline (w/v)	0.9% sterile saline for injection			
	1% Nu-3 in 0.9% saline (w/v)				
Formulation	2% Nu-3 in 0.9% saline (w/v)				
	5% Nu-3 in 0.9% saline (w/v)				
	10% Nu-3 in 0.9% saline (w/v)				

All study drug is provided in a 0.5 oz. oval low density ethylene dropper bottle. The bottle opening is plugged with a 13 mm extended controlled dropper tip and sealed with a 15/415 extend tip closure.

#### 10.2 **Dose Schedule**

The anticipated dosing plan is that each subject will receive a single topical administration of Nu-3 or Placebo on Day 1 followed by twice daily for 7 day administration of Nu-3 or Placebo on Day 2 as outlined in the following table. Actual randomization assignments and conduct of study may vary from this, as provided in 8.10 Safety Review.

	Nu-3 in 0.9% saline (w/v)					Total Dosed
Cohort	Dose 1 0.1%	Dose 2 1%	Dose 3 2%	Dose 4 5%	Dose 5 10%	Nu-3 + Placebo
1	8					10
2		8				10
3			8			10
4				8		10
5					8	10
						50

### 10.3 Drug Shipping, Packaging and Labeling

Study drug is shipped to the investigative site from in standard packing which consists of an outer shipping container (20 x 17 x 12.5), an inner container (12 x 12 x 6) and two foam inserts each holding a quantity of 25 vials. Ice is packed on the bottom and around all three sides of the foam containers. Contents of the label(s) will meet all applicable regulatory requirements.

Study drug is packaged in a 0.5 oz. oval low density ethylene dropper bottle plugged with a 13 mm extended controlled dropper tip and sealed with a 15/415 extend tip closure

The following draft label will be affixed to all containers of Nu-3 drug product, indicating the appropriate storage condition.

### **DRAFT LABEL**

GC: X; LID: X; CARTON	
Protocol #:	LAI2014-1
Product:	Bisphosphocin Nu-3 topical antibiotic or placebo
Bottle Number:	####
Lot Number*:	14K###
Directions for Use:	As directed, apply twice daily to the affected area
Storage:	Room Temperature^
Caution:	New Drug-Limited by federal law to Investigational Use Keep out of reach of children
Manufacturer:	Lakewood Amedex Inc., Sarasota, FL [name]

\*Lot number represents the group of kits being assembled for each cohort.

# 10.4 Study Drug Handling and Storage

### 10.4.1 **Handling and Storage**

Upon arrival of study drug shipping container at the investigative site, it is immediately opened by pharmacy personnel in a secure location, and contents are verified to match the shipping documentation.

Study drug is stored at the investigative site in a secure location routinely accessible only to Pharmaceutical Services personnel, under these environmental conditions: at ambient temperature.

### 10.4.2 **Study Drug Accountability**

The investigative site maintains records of study drug accountability and reconciliation throughout the course of the study. Records show the amount(s) of study drug received from Sponsor, administered to subjects, wasted/lost (with description of circumstances), and returned to Sponsor and/or Sponsor's designee. Only subjects enrolled and randomized in this study may receive study drug.

^Room temperature is defined according to the USP as the temperature that is prevailing in a work area.

#### 10.5 Randomization

Subjects are assigned to dosing with Nu-3 or Placebo according to the randomization schedule prepared prior to study start and provided by Sponsor/CRO. In the event that an expanded or unscheduled cohort is added, Sponsor/CRO will provide the randomization schedule for that cohort prior to admission of the cohort to the investigative site. The randomization scheme was predetermined and ordered in blocks of five (5). Five study kits are provided to each investigational site utilized to maintain the randomization scheme.

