#### Randomization

Randomization will be conducted in blocks of five to a ratio of 4:1 (active:placebo). Qualified subjects will be enrolled and randomized in: 8:8:8:8:8:10 ratio to either Nu-3 at one of five possible dose levels (0.1%, 1%, 2%, 5% and 10% Nu-3 solution in saline (w/v)), or to placebo, respectively.

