#### Test Kit

Test Product kits will be labelled and contain a 0.5 oz dropper bottle containing 15 mL of Test Product packaged in a cardboard carton with a foam insert for protection. These kits will be pre-labelled with kit numbers. The contents of the kits will not be known to the pharmacist, designee or clinical staff. Upon randomization of the subject, the pharmacist or designee will receive a randomization number along with a kit number that is available at that site. The kit with the corresponding kit number will be used for dose administration.

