### 8.4 Placebo Control

In each Cohort, 8 subjects will be randomized to receive Nu-3, and 2 subjects will be randomized to receive Placebo.

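### The protocol tells sites that blocks hold five subjects at 4:1 and that each site gets five kits, so identifying a block's one placebo subject reveals the others as Nu-3

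*Protocol*

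**What the plan says.** The block structure is stated twice in the current protocol. The synopsis (Randomization) says: "Randomization will be conducted in blocks of five to a ratio of 4:1 (active:placebo". Section 10.5 says the scheme was fixed in advance and "ordered in blocks of five (5", and continues: "Five study kits are provided to each investigational site utilized to maintain the randomization scheme". Section 8.4 gives the result for each cohort: "8 subjects will be randomized to receive Nu-3, and 2 subjects will be randomized to receive Placebo". Nothing in either document varies the block size or withholds it from sites, and section 21 shows that investigators sign the protocol.

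The trial is meant to be blind at site level. The synopsis (Test Kit) says: "The contents of the kits will not be known to the pharmacist, designee or clinical staff". Section 10.6 allows a code-break for an adverse event or a partner's pregnancy when knowing the treatment is likely to affect medical decisions, and also when the Safety Review Committee needs it. An investigator who has been unblinded then stops managing or assessing adverse events, but only for the subjects whose assignments were disclosed. Section 8.10.4 asks that any unblinding for safety review be kept as limited as possible.

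Under section 8.10.5.2, a Grade 2 or higher event is a DLT if it is "considered by the Investigator to be at least possibly related to study drug". SAP section 3 repeats the 4:1 ratio but gives no block size.

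**The concern.** A single fixed block size with one placebo per block links the assignments of the subjects who share the block. Once sites know the structure, information about one subject becomes information about the others, including subjects not yet dosed. Section 8.11 has subjects dosed one at a time.

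The safeguards in 8.10.4 and 10.6 work subject by subject. An investigator who learns that one subject had placebo is withdrawn from that subject's adverse event assessment. The same investigator can continue to assess the block-mates, who by deduction are now known to be on Nu-3.

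The stake is the primary safety objective. Under 8.10.5.1 one DLT among Nu-3 subjects expands the cohort and two stop escalation, so one or two relatedness judgements can decide the course of the study. The investigator also decides on Day 2, by looking at the ulcer, whether a patient continues (12.4). DFI scoring is subjective as well.

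**Working it through.** **Inputs.** Block of five (synopsis; 10.5). Ratio 4:1 (synopsis). Cohort allocation 8:2 (8.4). Overall allocation: "Qualified subjects will be enrolled and randomized in: 8:8:8:8:8:10 ratio" (synopsis). Five kits per site (10.5). Expansion by four subjects at 3:1 (8.10.5.1).

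**Reproducing the plan's allocation.** A block of five at 4:1 holds 5 × 1/5 = 1 placebo and 4 Nu-3. Two blocks give 8 Nu-3 and 2 placebo per cohort, as in 8.4. Ten blocks give 40 and 10, as in the synopsis (8 × 5 = 40, plus 10). One placebo per block is therefore exact.

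**If the placebo subject is identified.** None of the other four can be placebo, so each is Nu-3 with probability 4/4 = 1.00, against 0.80 beforehand.

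**If one Nu-3 subject is identified.** One placebo remains among four, so each block-mate's placebo chance is 1/4 = 0.25, against 0.20.

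**Which case a code-break meets.** If breaks are unrelated to arm, 10/50 = 20% show placebo and 80% show Nu-3. If the events that prompt a break are drug-related, placebo is less likely still.

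**Assignments known in advance.** Assume the placebo is equally likely at positions 1 to 5, the block is used in order, and the placebo is identified before the next subject is dosed. The mean number of later assignments then known is (4 + 3 + 2 + 1 + 0)/5 = 2. Later identification gives fewer.

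**Comparison after one placebo is identified:**

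| Structure | A given other subject is Nu-3 | Four given others are all Nu-3 |
|---|---|---|
| Disclosed blocks of five (same block) | 1.00 | 1.00 |
| One random 8:2 list over ten | 8/9 = 0.89 | 5/9 = 0.56 |
| No blocking | 0.80 | 0.8⁴ = 0.41 |

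In the second row one placebo remains among nine subjects. The four named subjects are all Nu-3 only if it falls among the other five.

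**Cost of giving up balance within each five.** Assume two sites take five subjects each under a random 8:2 list over ten. There are C(10,2) = 45 placements of the two placebos, and 2 × C(5,2) = 20 put both at one site. The probability is 20/45 = 44%. With blocks of five, one block per site, it is zero.

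**Expanded cohort.** Four subjects at 3:1 contain one placebo, so identifying it reveals the other three. This follows from the number and ratio in 8.10.5.1 and does not depend on a stated block length.

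**The case against.** The strongest reply is that certainty needs an uncommon event. Code-breaks are restricted. Most would show Nu-3, and those change almost nothing. Other protections narrow the route: kit contents are concealed, the kit number is given only at randomization, the schedule is in a sealed envelope, and the Safety Review Committee's unblinding is to spare site staff where possible. Site staff already expect Nu-3 with 80% probability. Identification affects one block only, and no figure in the documents links it to a change in DLT counts. All of this stands, and it limits the importance of the point. It does not close the gap, because none of these measures covers block-mates revealed by deduction.

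A reader might go further and infer that four subjects who seem to react at application would expose the fifth as placebo before enrolment. The documents do not support that. It would need four correct identifications. The patch test in protocol section 6 found 2% Nu-3 more irritating than saline on abraded skin but equal to it on intact skin, and nothing shows that a reaction identifies the assignment. If reactions did identify all four, the blind would already be lost for those four whatever the block size.

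Nor should a reader infer that every code-break reveals the block, or that a breach took place. Neither is shown.

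The deduction also requires a site to know which of its subjects share a block. The documents do not say outright that a site's five kits are one block. That is the natural reading of the kit sentence in 10.5, because the number equals the block length and the stated purpose is to maintain the scheme.

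**Conclusion.** The point holds as a conditional weakness. If the placebo subject in a block is identified, every other enrolled subject in that block is inferable as Nu-3 with certainty, up from 80%. That is four subjects in a full block and fewer in a partly used one. The cohort's other block is not revealed. If a Nu-3 subject is identified instead, the shift is only from 20% to 25%.

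This rests on 4:1 blocks of a single size, on sites reading the five kits as one block, and on someone at the site learning that a particular subject had placebo. The effect on relatedness judgements, and so on DLT counts, cannot be sized from the documents. The change is a low-priority improvement, worth making because the wording change costs almost nothing.

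**What to change.** Delete the block length from the synopsis (Randomization) and from 10.5, and delete the five-kits-per-site sentence from 10.5. Removing the block length alone would not be enough: five kits together with 8:2 still suggest one placebo per five. Keep only the 8:2 allocation per cohort in site-facing text, and move the block and kit-supply structure to a restricted randomization specification. The cost is protocol wording. Sample size, ratio and analysis do not change.

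Optionally, for cohorts not yet randomized, generate lists with an undisclosed structure that still gives 8:2. This requires new lists, because 10.5 says the schedule was prepared before study start, and the documents do not show which cohorts remain open. It also gives up some placebo balance between sites, by the 44% worked out above in the two-site example. The sponsor should state that trade-off if it takes this step.

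Two limits remain. What sites have already read cannot be recalled. Kits physically supplied in fives would still show the pattern unless the supply is changed too.

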### 10.6 Blinding and Unblinding

This is a double-blind study. The randomization schedule for each cohort is provided by Sponsor/CRO as a sequential list in a sealed envelope. At the investigative site, procedural precautions are taken to avoid unblinding due to visual inspection of Nu-3 and/or Placebo prepared for dosing.

Unblinding occurs only in the event of an Adverse Event, or pregnancy of a subject's partner, and only if knowledge of the administered study drug is judged likely to affect the medical treatment decisions related to the subject or pregnant partner, or if required for decision-making by the Safety Review Committee. In the event of unblinding, the Investigator notifies the Sponsor within 24 hours of breaking the blind and provides formal, written documentation to the Sponsor within 5 working days. This documentation includes the identity of the individual(s) who have become aware of randomization assignment(s), the date on which the blind was broken, and a description of the event motivating the unblinding. The Investigator also records in relevant source documents that blind was broken, reason for unblinding, and the date/time of that occurrence.

The Safety Review Committee may request unblinding to assist in Safety Review and decisions regarding further conduct of study. To the extent possible while meeting the need for appropriate Safety Review, the Investigator and other investigative site personnel are not unblinded. The existence of unresolved Adverse Events at the time of unblinding is given consideration. If an Investigator is unblinded, that Investigator is not subsequently involved in the management or assessment of AEs for Subjects whose dose assignments have been unblinded.

#### 10.7 **Study Drug Preparation**

Study drug is kept under supervision of pharmacy personnel until delivered to the area designated for study drug administration.

#### 10.8 **Study Drug Administration**

### 10.8.1 Study Drug Administration Procedure

Licensed Clinical Operations personnel at the investigative site administer each dose of Study Drug to study. Test Product will be administered to the infected diabetic foot ulcer and surrounding intact skin at a dose of 3 drops from a dropper bottle per 1 cm^2 of ulcer area.

After application of the Test Product is complete, the wound will be left open to air for 5 min and then will be dressed as per the following: Owens Gauze will be trimmed to cover the entire dimension of the ulcer and overlaid into the ulcer. Gauze dressings (2 x 2 inches) will be placed over the Owens Gauze to a depth of 1/4 inch followed by a circumferential wrap of

2 inch Kerlex. The dressing will be secured with paper tape applied to the circumferential dressing as to not come in contact with the underlying skin.

### 10.8.2 Disposition of Dose Administration Materials

Following study drug administration, materials possibly containing remaining visible study drug or Placebo solution are placed in a closed container and returned to the Pharmacy for storage at ambient temperature until shipped to the Sponsor.

